1.0 Research Design

1.1 Purpose/Specific Aims

The current study seeks to understand factors that influence college students' likelihood of participating in the National Marrow Donor Program (NMDP)/Be the Match for bone marrow and stem cell donations. The secondary aim is to compare emotional and rational approaches to encouraging participation in the registry and how these approaches may impact intentions to participate in the NMDP.

A. Objectives

1. The study will describe the role of demographic, personality, and psychosocial factors in attitudes towards participating in the National Marrow Donor Program.
2. Two strategies for increasing motivation (emotional appeal or factual data on racial/ethnic disparities in representation on the registry) for enrollment will be tested.
3. Strategies for enrollment will be compared by Race and Ethnicity to understand the best approaches to recruiting diverse students into the registry program.

B. Hypotheses / Research Question(s)

Approximately 12,000 patients need a bone marrow transplant each year to treat their cancer or other hematologic condition, but only about 30% of these patients find matches within their families (National Marrow Donor Program, 2013). The NMDP maintains a list of potential donors through the "Be the Match" organization which often runs donor drives on college campuses. Bone marrow donors are matched on genetic similarities, making race and ethnicity an important component in finding a match between a patient and a potential donor. Donors registered with Be the Match are 67% White, making it more difficult for individuals of color to find good matches, which may delay transplants and ultimately impact survival and the success of transplants. Thus, diversity is an important component of enrolling potential donors in the transplant registry. Because the student body of Rutgers Camden is diverse and within the age range targeted to join the NMDP, understanding psychological factors that contribute to participation and the most effective strategies to cultivate enrollment intentions is an important step towards enhancing the diversity of the donor registry and improving health outcomes for patients of color.

1. It is hypothesized that students who report high levels of altruism will be more likely to report an intention to enroll in the stem cell transplant registry.
2. It is hypothesized that students who report high levels of knowledge about stem cell transplants will be more likely to report an intention to enroll in the stem cell transplant registry.
3. It is hypothesized that high altruistic students will be more likely to enroll when presented with an emotional appeal.
4. It is hypothesized that high knowledge students will be more likely to enroll when presented with a factual appeal.
5. It is hypothesized that the rational appeal which focuses on health disparities will result in a higher likelihood of enrollment for students of color as compared to white students.
6. It is hypothesized that self-esteem will differ between individuals who do and do not indicate an intention to enroll in the registry.

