Knowledge about the bone marrow and stem cell donation process and how this information is communicated also appear to be important factors in whether participants enroll in the registry. Research in college students studying medically related fields has demonstrated that students hold many misconceptions about the donation process and those students with lower knowledge were less likely to indicate an intention to enroll (Vasconellos Nunes, & Feller, 2011). Further, knowledge about the process is generally higher in medical students who are enrolled in the registry (Narayaman et al., 2016). As knowledge is generally low even among students with medically-oriented training, understanding how to best communicate about the NMDP to a general college audience is important. Specifically, emotional appeals have been found to be more effective in motivating participation in transplant registries when compared to rational approaches that presented statistics and facts about the transplant process (Studts et al., 2010). Emotional appeals that help participants envision specific patients and the positive outcomes of their donation may be especially important in increasing the likelihood that an enrolled individual follows through with the donation when asked (Vekaria et al., 2020). What is not known though is how a rational appeal that includes information regarding the need for diversity may affect participation, especially in individuals from diverse backgrounds. To date, these different approaches to communicating information about bone marrow registries have not been studied in diverse college students.

Demographic factors, such as race and ethnicity, are also important predictors as evidenced by the lower likelihood of finding a match for individuals of color suggesting a need for greater diversity in the registry (National Marrow Donor Program, 2013). Older research suggests that a willingness to donate does not differ between African Americans and White individuals, but White individuals may be more familiar with the registry, which in turn leads to greater participation rates (Onitilo et al., 2004). Women may also be more willing to register (Studts, et al., 2010), although this predictor is not consistent across all studies (Monaghan et al., 2020). Family cancer history is also an important factor in the likelihood of participating (Studts, et al., 2010).

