1.3 Research Design and Methods

A. Research Procedures

This study is a randomized controlled trial that will randomize participants to receive either an emotional appeal about a child with cancer who needs a bone marrow transplant or a rational appeal using data on the racial/ethnic disparities within the transplant registry. (See Appendix A for condition prompts).

Participants will be recruited through the Psychology Subject Pool through the SONA system which will then link students to the study measures in Qualtrics. Participants will be asked their age to confirm eligibility to participate (students must be between 18-35) and eligible students will be presented with the consent form in Qualtrics. Participants will then be asked to complete measures of demographic information, personality/psychological characteristics, and transplant-related knowledge, intentions, and attitudes. All participants will then be given background information on bone marrow transplants (See Appendix A for text).

Randomization: Students will be randomized by sex in Qualtrics to the emotional presentation condition or the rational presentation condition. The emotional condition will tell the story of a fictional pediatric patient with cancer who needs a transplant. The rational condition will describe the facts about the need for diversity in the registry (See Appendix A for condition prompts).

After being presented with the rational or emotional appeal, participants will again be asked their intentions to register, their motivations for registering, and their mood.

B. Data Points

Study data will include demographic information and responses to questionnaires given during the survey in Qualtrics.

C. Study Duration

Participation will last approximately 30 minutes.

D. Endpoints

The study will continue to collect data until a sufficient sample size is accrued.

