1.5 Sample Size Justification

Prior research has demonstrated an effect size of $w=0.38$ (medium effect) between an emotional and rational appeal, thus we expect a medium effect size (Studts et al., 2010). In order to compare the effect of the two conditions (emotional/rational) by race/ethnicity (White, African-American, Latinx considered as the primary groups represented, recognizing there will be others) we will need 300 participants to have 85% power to detect a medium effect with a p-value of 0.05. To be conservative and ensure we have a large enough sample of each race/ethnicity group, we will seek to enroll 400 students.

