History of transplant/donation	Previous research by Narayanan et al., (2016) has included these 15 items to assess an individual's familiarity with the transplant and donation process.
Motivations to donate	Participants are asked to rank order 11 possible reasons that they may decide to register for the transplant registry (Bart et al., 2014). Participants will complete this measure before and after the Emotional/Rational condition presentation.
Attitudes towards bone marrow transplant	Participants will be asked 9 questions about their attitudes towards joining the bone marrow registry and donating stem cells at a later date. This measure has been used in previous research (Narayanan et al., 2016).
Ambivalence	The Simons Ambivalence Scale is a 7-item scale developed to assess feelings about solid organ donation(Gardner, 1987). The measure has been modified for stem cell donor participation (Fingerut et al., 2020) and 4 of the 7 items will be used in the current study.

B. Dependent Variables or Outcome Measures

The primary dependent variable is intentions to register in the bone marrow transplant registry.

Secondary Dependent Variables: Participants will be asked about how factual and how emotional they perceived the appeal they received is to determine if the manipulation worked. We will also ask about their current mood again.

Construct/Measure	Description
Intentions to register	Participants will be asked 2 questions about whether they will register and the rate the likelihood of registering. They will be asked these questions before and after the experimental manipulation.
Manipulation Check	Participants will be asked to rate how emotional and how factual the appeal they received was on a 1-7 scale.
Mood	Participant mood will be assessed pre/post survey, asking participants to rate their current mood on a 1-10 scale.

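### Hypothesis 5 compares students of color with White students under the rational appeal alone, so a prior difference in intention can mask or mimic the appeal's effect, and section 6.1 names no deciding contrast

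*Combined protocol and SAP*

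**What the plan says.** Hypothesis 5 in section 1.1 B concerns the disparity-focused rational message only, and predicts that it "will result in a higher likelihood of enrollment for students of color as compared to white students". The emotional appeal does not appear in it.

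Two other places describe a different comparison. Objective 3 in section 1.1 A reads: "Strategies for enrollment will be compared by Race and Ethnicity to understand the best approaches to recruiting diverse students into the registry program". Section 1.5 sizes the trial to "compare the effect of the two conditions (emotional/rational) by race/ethnicity", with three main groups, and states: "we will need 300 participants to have 85% power to detect a medium effect with a p-value of 0.05". The target is then raised to 400.

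Section 6.1 is one sentence naming ANOVAs and linear regression. It assigns no model, contrast, interaction term or covariate to any hypothesis.

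Three further facts bear on the point:
- Intention to register is covered by two items, one on whether the student will register and one rating the likelihood. Section 1.6 B says: "They will be asked these questions before and after the experimental manipulation".
- In section 1.3 A, after the first measures and before the appeal, "All participants will then be given background information on bone marrow transplants".
- Section 1.2 reports from older research that "a willingness to donate does not differ between African Americans and White individuals", but that "White individuals may be more familiar with the registry, which in turn leads to greater participation rates".

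**The concern.** Only the appeal is randomised. Within the rational arm, students of color and White students differ by whatever separated them beforehand as well as by how they respond to the appeal. Hypothesis 5 attributes the whole difference to the appeal. If White students start with higher intention, a real differential benefit can be missed. If students of color start higher, a difference can appear when the appeal works equally in both groups.

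The contrasts that randomisation supports are emotional versus rational within each race/ethnicity group, and the difference between those contrasts. The first answers Objective 3 directly. The second asks whether the relative merit of the appeals depends on race/ethnicity.

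Because section 6.1 is silent, two analysts could test different quantities under hypothesis 5, and both could claim to follow the protocol. The choice could be made after the data are seen. The overall emotional-versus-rational comparison is not affected.

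**Working it through.** **The plan's own figure.** Section 1.5 gives 300 students for 85% power at 0.05 and does not name the contrast. Take a 1-df chi-square test, a conventional medium effect of w = 0.30 (assumed) and 100 students. The noncentrality is 100 × 0.30² = 9 and power is 85.1%. Three groups of 100 make 300. The figure therefore matches an appeal comparison within each of three race/ethnicity groups; this is inferred, not stated. At the cited w = 0.38 the same test with 100 students has 96.7%. The match is neither to hypothesis 5 as worded nor to an interaction.

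**Assumed inputs.** The documents give no prior gap, race split, allocation ratio or pre-post correlation. I take N = 400 (section 1.5), 200 per arm, one third White, a continuous outcome with SD 1, a true extra benefit of the rational appeal for students of color of 0.5 SD, a prior gap that is the same before and after, and a two-sided 0.05 test by normal approximation.

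**Test as worded (rational arm, no baseline).** SE = √(1/66.7 + 1/133.3) = 0.150. The expected difference is 0.5 minus the White lead. The chance of a significant result favoring students of color is Φ(difference/SE − 1.96).

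| White lead (SD) | Expected difference | Chance |
|---|---|---|
| 0 | 0.5 | 92% |
| 0.1 | 0.4 | 76% |
| 0.2 | 0.3 | 52% |
| 0.3 | 0.2 | 27% |

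The reverse follows from the same formula. With no differential effect and a prior lead of 0.2 or 0.3 SD for students of color, the test supports hypothesis 5 in 27% or 52% of trials, against a nominal 2.5%.

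**Condition by race/ethnicity interaction.** The prior gap is present in both arms and cancels. SE = √2 × 0.150 = 0.212, and power is Φ(0.5/0.212 − 1.96) = 65% at any lead. At N = 300 the SE is 0.245 and power 53%. With pre-appeal intention as covariate, the SE is multiplied by √(1 − r²): power at N = 400 is 70%, 78% and 91% for r = 0.3, 0.5 and 0.7.

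**Rational-arm test that does use baseline.** This is the fair comparator for the adjusted interaction.
- Change score: SE = 0.150 × √(2(1 − r)), and the lead cancels. Power is 80%, 92% and 99% at r = 0.3, 0.5 and 0.7, at any lead.
- Covariate adjustment at r = 0.5: SE = 0.150 × √0.75 = 0.130. The expected difference is 0.5 − lead × (1 − r), so half of the lead remains. Power is 97%, 87% and 77% at leads of 0, 0.2 and 0.3 SD.

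These figures hold only if the two groups respond equally to the background text, which falls between the first intention measure and the appeal. Any difference in that response stays in the within-arm change in full and cancels only against the emotional arm.

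**Precision within a group.** With 67 students per arm in one race/ethnicity group (one third of 400), the 95% CI half-width for the appeal difference is 1.96 × √(2/67) = 0.34 SD.

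**The case against.** **The masking arises only if baseline is ignored.** This largely stands. Pre-appeal intention is collected from everyone, and a rational-arm test that uses it avoids most or all of the loss. From the falls to 52% and 27%, a reader might infer that the interaction is the more powerful test whenever White students lead. That holds only against the unadjusted test. Against a baseline-adjusted or change-score test in the rational arm, the interaction has no such advantage in these figures. The case for it is validity: it alone removes a race difference in response to the shared background text. No such difference is documented or quantified.

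**A White lead is not established.** This stands. Section 1.2 reports no difference in willingness, which is the construct closest to the outcome. The reported advantage is in familiarity and participation, and the background text might narrow it. The documents do not suggest a lead for students of color either.

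**Hypothesis 5 may simply mean moderation.** It may. Objective 3 and section 1.5 point that way, and ANOVA or regression can carry an interaction. A reader might infer that section 6.1 commits to the wrong test. It does not; it is compatible with both readings. The fix would then write down what was meant.

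**The interaction does not isolate the rational appeal.** This stands. Both arms receive an appeal, so a positive interaction could mean that the emotional story works less well for students of color.

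**Conclusion.** The concern holds. Hypothesis 5 as worded attributes a comparison of non-randomised groups to the appeal, and the plan neither names the deciding contrast nor says whether baseline is used. It is worth correcting before analysis because a choice made afterwards would not be credible.

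The size is conditional. Under the assumptions above, the unadjusted worded test drops from 92% to 52% and 27% as an assumed White lead goes from 0 to 0.2 and 0.3 SD. The interaction stays at 65%, or 78% with the covariate at r = 0.5. The documents supply none of the lead, the 0.5 SD benefit, the race split or r, and the figures do not transfer to a yes/no intention item.

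A reader might go further and conclude that the trial will miss a real effect, or that its overall appeal comparison is compromised. The documents support neither conclusion.

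**What to change.** - **Section 1.1 B:** restate hypothesis 5 as a difference between race/ethnicity groups in the rational-versus-emotional effect.
- **Section 6.1:** decide it by the condition by race/ethnicity term in a model of post-appeal intention, with pre-appeal intention as covariate. Name which of the two intention items is modeled. If it is a yes/no item, state the scale, because an interaction can differ between risk differences and odds ratios.
- **Reporting:** give the emotional-minus-rational difference with 95% CI within each group as the direct answer to Objective 3. Draw no conclusion about the appeals from race comparisons within one arm.
- **Grouping:** before analysis, define whether two groups (hypothesis 5) or three (section 1.5) are used, and where other students go.
- **Stated limit:** with no arm free of an appeal, the interaction shows the benefit of rational relative to emotional, not the effect of the rational appeal alone.
- **Section 1.5:** state which contrast the 85% refers to, and add interaction power over a range of effects.

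Treating hypotheses 3 and 4 in the same form, ranking them or sharing alpha is optional and not part of this change.

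Cost: wording only, with no new data or students. The downside is power. With no prior gap, the unadjusted interaction has 65% against 92% for the worded test. At 0.5 SD and one third White, 85% power without adjustment would need about 647 students: SE = 0.5/(1.96 + 1.036) = 0.167, and 9/0.167² is about 323 per arm. The covariate recovers part of this, by an amount that depends on r.

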1.2 Research Significance

Previous international research has demonstrated that the potential to save lives is the most motivating factor in the decision to enroll in bone marrow registries while the biggest barriers are lack of information on the process and risks (Bart et al., 2014). Qualitative research supports that personality characteristics

such as altruism are important influences on intentions to register with NMDP and to later donate (Kaster et al., 2014) and altruism is described as central to the decision-making process in those who have gone through with donations (BIIlen, Madrigal, Scior, Shaw & Strydom, 2017). However, when examining the relationship between altruism and intentions to enroll in the NMDP in a sample of medical students, altruism was not related to intentions (Narayaman et al., 2016). Self-esteem has also been implicated in charitable donations (Surana & Lomas, 2014) and bone marrow donors report more positive sense of self post-donation (Butterworth et al., 1993), but self-esteem has not been examined as a correlate of decision making to participate in bone marrow registries. Thus, the role of personality characteristics in motivating participation in the NMDP are unclear but may be important correlates to consider.

Knowledge about the bone marrow and stem cell donation process and how this information is communicated also appear to be important factors in whether participants enroll in the registry. Research in college students studying medically related fields has demonstrated that students hold many misconceptions about the donation process and those students with lower knowledge were less likely to indicate an intention to enroll (Vasconellos Nunes, & Feller, 2011). Further, knowledge about the process is generally higher in medical students who are enrolled in the registry (Narayaman et al., 2016). As knowledge is generally low even among students with medically-oriented training, understanding how to best communicate about the NMDP to a general college audience is important. Specifically, emotional appeals have been found to be more effective in motivating participation in transplant registries when compared to rational approaches that presented statistics and facts about the transplant process (Studts et al., 2010). Emotional appeals that help participants envision specific patients and the positive outcomes of their donation may be especially important in increasing the likelihood that an enrolled individual follows through with the donation when asked (Vekaria et al., 2020). What is not known though is how a rational appeal that includes information regarding the need for diversity may affect participation, especially in individuals from diverse backgrounds. To date, these different approaches to communicating information about bone marrow registries have not been studied in diverse college students.

Demographic factors, such as race and ethnicity, are also important predictors as evidenced by the lower likelihood of finding a match for individuals of color suggesting a need for greater diversity in the registry (National Marrow Donor Program, 2013). Older research suggests that a willingness to donate does not differ between African Americans and White individuals, but White individuals may be more familiar with the registry, which in turn leads to greater participation rates (Onitilo et al., 2004). Women may also be more willing to register (Studts, et al., 2010), although this predictor is not consistent across all studies (Monaghan et al., 2020). Family cancer history is also an important factor in the likelihood of participating (Studts, et al., 2010).

Our student body at Rutgers University Camden is very diverse and typically within the age range targeted by Be the Match, making it an important group to understand demographic, personality, and message communication factors that contribute to the likelihood of participation in the registry.

1.3 Research Design and Methods

A. Research Procedures

This study is a randomized controlled trial that will randomize participants to receive either an emotional appeal about a child with cancer who needs a bone marrow transplant or a rational appeal using data on the racial/ethnic disparities within the transplant registry. (See Appendix A for condition prompts).

Participants will be recruited through the Psychology Subject Pool through the SONA system which will then link students to the study measures in Qualtrics. Participants will be asked their age to confirm eligibility to participate (students must be between 18-35) and eligible students will be presented with the consent form in Qualtrics. Participants will then be asked to complete measures of demographic information, personality/psychological characteristics, and transplant-related knowledge, intentions, and attitudes. All participants will then be given background information on bone marrow transplants (See Appendix A for text).

Randomization: Students will be randomized by sex in Qualtrics to the emotional presentation condition or the rational presentation condition. The emotional condition will tell the story of a fictional pediatric patient with cancer who needs a transplant. The rational condition will describe the facts about the need for diversity in the registry (See Appendix A for condition prompts).

After being presented with the rational or emotional appeal, participants will again be asked their intentions to register, their motivations for registering, and their mood.

B. Data Points

Study data will include demographic information and responses to questionnaires given during the survey in Qualtrics.

C. Study Duration

Participation will last approximately 30 minutes.

D. Endpoints

The study will continue to collect data until a sufficient sample size is accrued.

